12.2 Measurement of Aromatase Inhibitor-Induced Arthralgia

Many trials which specifically examine AIA or other joint pathologies use a widely validated clinical tool termed the Health Assessment Questionnaire (HAQ-II). It is commonly used in rheumatology literature, and has been substantiated across many trials. This is a simple survey, which is a proven, reliable, and accurate indicator of joint pains and consequent disabilities (14) (15). An abbreviated version of the HAQ-II, which takes about 5 minutes to complete, will be used in the study (see Appendix A).

This questionnaire asks 20 questions in 8 categories of functioning: dressing, rising, eating, walking, hygiene, reach, grip, and usual activities. For each question, the patient is scored on a scale of 0-3, depending on how much difficulty they have performing the task. A score of 0 correlates with no difficulty at all, and a score of 3 denotes that the patient is unable to do the task. The highest numerical score from each category is used, and the average of these 8 numbers is the composite score on the HAQ-II. Scores of 0-1 are considered to represent mild to moderate difficulty, 1-2 represents moderate to severe disability, and 2-3 represents severe to very severe disability. Average score in a population based study is 0.49, whereas patients with osteoarthritis and rheumatoid arthritis have average scores of 0.8 and 1.2, respectively. Most investigators agree that “minimal clinical important difference” is 0.2 (42). Thus, the study uses this as a cut-off point.

The visual analog scale is the other major component of the HAQ-II. In this, the patient is asked to mark, with a vertical line, where their pain lies on a horizontal line which is 15 cm long, with the far left side of the line representing no pain at all, and the far right side representing unbearable pain. To obtain the individual’s score, the distance between the far left side of the line and the patient’s mark is multiplied by 0.2. This converts the number of centimeters into the appropriate score and will yield a value from 0 to 3.

For the purposes of this study, AIA will be defined as any of the following criteria: 1) increase in HAQ-II score from baseline by 0.2 or greater; or 2) increase in visual analog pain score by 0.3 or greater. The HAQ-II questionnaire and its visual analog pain score are used in the definition of

AIA because the questionnaire has been validated through many other studies which examine joint pain, and it is very simple to do in the office in less than 5 minutes. Though grip strength will be measured at various time points throughout the study, it will only be used in the exploratory analysis to see whether it may be an appropriate measure for AIA. Grip strength measurement is a relatively easy, inexpensive, objective criteria which may help to more clearly define AIA. This data will be very useful in the future, as it may serve to support a clearer, more objective definition of AIA for use in future studies, and for use in clinical practice.

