2.3 Exploratory Objective

- 2.3.1 To study whether grip strength may serve as an accurate and reliable objective measure to complement the subjective complaint of AIA.
- 2.3.2 To investigate whether high dose vitamin D may be associated with lower breast cancer recurrence than standard dose Vitamin D

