10. CORRELATIVE/SPECIAL STUDIES

10.1 Grip Strength

To further investigate whether grip strength may serve as a simple, objective measure of AIA, we will measure grip strength at baseline, week 12 and week 52 visits (see study Calendar in Appendix B), and see whether changes in grip strength do correlate with changes in joint pain, as represented in the HAQ score. Research coordinators will measure grip strength as outlined in [Section 6.8.2](#).

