13.2 Sample Size/Accrual Rate

The primary objective of this study is to determine if supplementation of high dose Vitamin D prevents AIA in women being treated with adjuvant aromatase inhibitors. The Health Assessment Questionnaire II (HAQ-II) will be used to assess joint pain symptoms. Previously published estimates of AIA incidence showed that 33% of women on standard dose of vitamin D, and 19% of women on a high dose of vitamin D, developed AIA (43). Assuming a one-sided test with $\alpha=0.10$, $\beta=0.20$, we would need 93 women in each arm to detect a different rate of AIA development using the Chi-square test. Assuming 5% dropout rate in the first 12 weeks, we will accrue 93 women to each arm, for a total of 186 women. Sample size calculations were conducted using nQuery Advisor 7.0, Statistical Solutions, USA. Given that there are over 8000 office visits each year in our Baylor Clinic and Smith Clinic, we should easily be able to recruit an average of 4-6 women/month to the study, which would allow us to complete accrual in approximately 3 years.

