13.4 Primary Endpoint

Descriptive and summary statistics will be computed for all demographic and clinical data in each treatment group. The HAQ-II will be used to assess joint pain symptoms; a higher score indicates more severe joint pain. Scores will be evaluated for the development of AIA between baseline and Week 12, as well as between baseline and Week 52, though development of AIA at 12 weeks will be the primary endpoint. The scores will be dichotomized as “development of AIA” (as defined above, in Section 12.2) or “no development of AIA.” Group differences in AIA rate will be assessed using the Chi-square test. Development of AIA at week 12 will be used to test the primary objective. The week 52 data will be measured and reported as well. As exploratory analyses, development of AIA will be assessed using logistic regression, adjusting for potential confounders such as age at diagnosis, race/ethnicity, BMI, receipt of chemotherapy, taxane use, and use of hormone replacement therapy. All statistical tests are one-sided with $\alpha = 0.10$ as the level of significance.

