13.6 Exploratory Endpoints

For each patient on the study, grip strength will be correlated with AIA score using logistic regression analysis and Spearman correlation at three time points throughout the study – baseline, week 12, and week 52. At five years, we will also compare breast cancer recurrence rates in each arm using Kaplan-Meier survival analysis and log-rank test.

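### Objective 2.3.1 asks whether grip strength is an accurate measure to complement the complaint of AIA, but section 13.6 plans only association statistics, which do not measure accuracy.

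*Combined protocol and SAP*

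**What the plan says.** Section 2.3.1 sets the exploratory objective: "To study whether grip strength may serve as an accurate and reliable objective measure to complement the subjective complaint of AIA". Section 12.2 keeps AIA defined by the HAQ-II score and its pain scale. Of grip strength it says that "it will only be used in the exploratory analysis to see whether it may be an appropriate measure for AIA", and it hopes that in future "it may serve to support a clearer, more objective definition of AIA for use in future studies, and for use in clinical practice".

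The analysis is given in two places. Section 13.6 says that "grip strength will be correlated with AIA score using logistic regression analysis and Spearman correlation at three time points throughout the study", namely baseline, week 12 and week 52. Section 10.1 will "see whether changes in grip strength do correlate with changes in joint pain, as represented in the HAQ score".

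The only significance level is in section 13.4, on the primary endpoint: "All statistical tests are one-sided with" an alpha of 0.10. Section 13.6 states no level or direction of its own.

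Neither document section nor appendix plans an AUC, a sensitivity, a specificity, a cut-off for grip, or a target value for any of these.

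**The concern.** Whether a measure is accurate is a question of discrimination: how far the grip changes of women with AIA are separated from those of women without it. An odds ratio or a correlation that differs from its null value shows that the two are related. It does not show that the relation is strong enough to help define the condition, and in a sample of this size a weak relation is readily significant.

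At stake is how the grip result is read. With no accuracy statistic in the plan, the p-value and the size of an odds ratio or correlation are all that the reader is promised. A significant association could be taken as support for a future definition of AIA that would in fact miss many affected women or flag many unaffected ones. The primary and secondary analyses are not touched.

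**Working it through.** **The plan's own figure.** The documents give no power or accuracy figure for grip. The trial's base sample size does reproduce. With 33% v 19%, one-sided 0.10, power 0.80 and pooled variance under the null:

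n = [1.2816·√(2·0.26·0.74) + 0.8416·√(0.33·0.67 + 0.19·0.81)]² / 0.14² = 87.6, so 88 per group; 88/0.95 = 92.6, so 93.

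**Inputs for the grip check**
- 186 women: sections 3 and 13.2. (Section 13.7 gives 196; I use 186.)
- AIA in 26%, the midpoint of the 33% and 19% in section 13.2: 0.26 × 186 = 48 with AIA, 138 without.
- Grip change normal with equal SD in both groups (binormal model): my assumption.
- Odds ratio per SD: not in the documents. I take 1.5, with 1.35 and 2.0 as a range.
- Specificity: not in the documents. I take 70%, 80% and 90%.

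**Formulas**
- Separation in SD units: d = ln(OR per SD)
- Probability of significance: Φ(d·√(n₁n₀/N) − z), with z = 1.2816 (one-sided 0.10) or 1.96 (two-sided 0.05)
- AUC = Φ(d/√2)
- Sensitivity at specificity s = Φ(d − z_s), with z_s = 0.524, 0.842, 1.282 for 70%, 80%, 90%

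**Odds ratio 1.5.** d = 0.4055 and √(48·138/186) = 5.968, so d·5.968 = 2.420.
- One-sided 0.10: Φ(2.420 − 1.282) = 0.872
- Two-sided 0.05: Φ(2.420 − 1.96) = 0.677
- AUC: Φ(0.287) = 0.613
- Sensitivity: Φ(−0.119) = 0.453, Φ(−0.436) = 0.331, Φ(−0.876) = 0.190

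| OR per SD | Significant, one-sided 0.10 | Significant, two-sided 0.05 | AUC | Sensitivity at 80% specificity |
|---|---|---|---|---|
| 1.35 | 0.695 | 0.433 | 0.584 | 0.294 |
| 1.5 | 0.872 | 0.677 | 0.613 | 0.331 |
| 2.0 | 0.998 | 0.985 | 0.688 | 0.441 |

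**Sensitivity to the inputs (OR 1.5, one-sided 0.10).** With 5% dropout (46 and 130 women): Φ(0.4055·5.829 − 1.282) = 0.86. With AIA in 19% (35 and 151): Φ(0.4055·5.330 − 1.282) = 0.81. With AIA in 33% (61 and 125): Φ(0.4055·6.403 − 1.282) = 0.91. The AUC does not depend on these numbers.

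**Check by simulation.** For a nearly identical separation (d = 0.411, which is sensitivity one third at 80% specificity), 186 women and 1,000 runs, the logistic Wald test was significant in 87.8% of runs and the Spearman test in 87.3%.

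**Precision of the proposed statistics with 48 cases.** By the Hanley–McNeil formula at AUC 0.613, SE = 0.049 and the 95% half-width is 1.96·0.049 = 0.095, about 0.10. For a sensitivity of one third: 1.96·√(0.333·0.667/48) = 0.133, about 13 points.

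**The case against.** The strongest reply is that the plan claims little. The analysis is labelled exploratory, the aim is a measure that complements the complaint rather than replaces it, and correlation with the patient-reported score is an ordinary first step. Logistic regression and Spearman also yield effect sizes, so a weak relation would be visible. Nothing bars a later AUC from the same data. All of this stands, and it keeps the point minor. It does not turn association into a measure of accuracy, which is the word that the objective uses.

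A reader might go further and infer that the trial would probably declare grip strength supported even if it missed two thirds of AIA cases, and that the lenient one-sided 0.10 level is to blame. The documents do not support that reading, for three reasons.
- No section ties a p-value to a conclusion about grip; sections 10.1 and 13.6 only say that it will be correlated.
- Missing two thirds is not a property of the measure. It follows from choosing 80% specificity. At 60% specificity the same odds ratio of 1.5 gives sensitivity Φ(0.405 − 0.253) = 56%. If grip were instead dichotomised, a measure with sensitivity one third would be significant at one-sided 0.10 with probability 71% at 80% specificity, but only 44% at 75% and 20% at 70%.
- The level is not the cause. At two-sided 0.05 the odds ratio of 1.5 is still significant with probability 68%. It is also open to question whether the sentence in section 13.4 was meant to govern section 13.6.

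**Conclusion.** The concern holds in a limited form. The planned statistics cannot answer the accuracy part of objective 2.3.1, whatever the data show. Under the binormal model with 186 women and 26% AIA, an odds ratio of 1.5 per SD is significant with probability about 87% at one-sided 0.10, or 81% to 91% as the AIA rate runs from 19% to 33%. Its AUC is only 0.61. So a significant association could be read as support for a poorly discriminating measure.

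That reading is a risk of interpretation, not a rule in the plan. The odds ratios, the distribution and the specificities are assumptions, since the documents give no figures for grip. The consequence is confined to an exploratory objective, so this is a desirable improvement rather than a necessary one.

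**What to change.** In section 13.6:
- Make the main exploratory grip analysis the AUC, with 95% CI, of grip change from baseline to week 12 for observed week-12 AIA. Leave out women whose AIA is only assumed under section 12.1.2 because the week-12 HAQ is missing.
- Report sensitivity with 95% CI at fixed specificities such as 70%, 80% and 90%. This avoids needing a grip-decline threshold, which the documents do not supply. Because the cut-offs would then be estimated from the data, a bootstrap interval is suitable.
- Base the statement on accuracy under objective 2.3.1 on these results, and keep the logistic regression and Spearman correlation as description.

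The cost is a few lines of wording and analysis. Grip strength and the HAQ are already measured at baseline and week 12. The downsides are limited precision with about 48 cases (half-width about 0.10 for the AUC and about 13 points for sensitivity) and a conclusion on grip strength that may be less favourable than a significant p-value would suggest.

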12.3 Compliance with AI therapy

Compliance with aromatase inhibitor therapy will be evaluated by a physical pill count at the scheduled clinic visits on Weeks 12, 24, 36, and 52. Subjects will be instructed to bring their used bottles of aromatase inhibitor to each return visit, along with any unused tablets. Study staff will count the number of remaining tablets at each visit to assess compliance. In the event that the subject forgets to bring their used study meds to their clinic visit, compliance will be assessed by direct questioning of the subject. In this case, subjects should be counseled to bring their used drug bottles to their next scheduled clinic appointment so that compliance may be confirmed by pill count. Subjects should be instructed to report any missed doses of aromatase inhibitor to the study coordinator.

Compliance with the aromatase inhibitor will be calculated by the ratio of number of pills actually taken to the number of pills that should have been taken. Compliance will be defined as a ratio ≥ 0.80 . Study staff should ensure subject understanding of dosing instructions for subjects whose compliance is less than 100%. In addition, the importance of compliance with anticancer therapy should be reinforced. In the case of non-compliance, the study coordinator will ascertain, from the patient, the main reason for the non-compliance, and this will be recorded as study data.

Subjects who miss doses as a result of physician-prescribed drug holidays will not be considered non-compliant. Calculation of the compliance ratio should thus be adjusted such that the “number of pills that should have been taken” reflects the drug holiday.

13. STATISTICAL CONSIDERATIONS

13.1 Study Design/Endpoints

The primary endpoint will be development of aromatase inhibitor induced arthralgia. Secondary endpoints will be compliance with aromatase inhibitor therapy and baseline vitamin D level.

Exploratory endpoints will be grip strength and breast cancer recurrence. Women on the study will be randomized to receive either high dose vitamin D or standard dose vitamin D for a total of 52 weeks (see attached [Schema](#)). All women will have their arthralgia and vitamin D levels assessed periodically throughout the study.

13.2 Sample Size/Accrual Rate

The primary objective of this study is to determine if supplementation of high dose Vitamin D prevents AIA in women being treated with adjuvant aromatase inhibitors. The Health Assessment Questionnaire II (HAQ-II) will be used to assess joint pain symptoms. Previously published estimates of AIA incidence showed that 33% of women on standard dose of vitamin D, and 19% of women on a high dose of vitamin D, developed AIA (43). Assuming a one-sided test with $\alpha=0.10$, $\beta=0.20$, we would need 93 women in each arm to detect a different rate of AIA development using the Chi-square test. Assuming 5% dropout rate in the first 12 weeks, we will accrue 93 women to each arm, for a total of 186 women. Sample size calculations were conducted using nQuery Advisor 7.0, Statistical Solutions, USA. Given that there are over 8000 office visits each year in our Baylor Clinic and Smith Clinic, we should easily be able to recruit an average of 4-6 women/month to the study, which would allow us to complete accrual in approximately 3 years.

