3. STUDY DESIGN/SUMMARY

This is a randomized, multi-center, controlled, phase II study comparing high dose vitamin D vs. standard dose vitamin D for post-menopausal breast cancer patients who are beginning adjuvant aromatase inhibitor therapy. The study is intended to be conducted in up to 5 centers within the U.S.A which are routinely engaged in the administration of aromatase inhibitor therapy for the study specified population. All patients who are starting an AI in the adjuvant setting are eligible to participate in the study.

In order to preserve power and compensate for the interim futility analysis which tends to reduce power, the sample size of the study is increased from 88 per group to 93 per group, which is 186 total if considering a 5% drop out rate. A total of 186 patients at up to 5 centers will be randomized 1:1 to receive either 50,000 International Units (IU) oral vitamin D per week for 12 weeks followed by 2000 IU daily for 40 weeks, or 800 IU Vitamin D daily for 52 weeks. All women on both arms of the trial will also take calcium carbonate 600 mg daily.

The primary endpoint for this study is development of AIA in each arm after 12 weeks of AI therapy, as determined by patient questionnaires. Secondary endpoints include compliance with AI therapy, as well as correlation of low baseline vitamin D levels with development of AIA. Grip strength is an exploratory endpoint.

[figure not shown]
Throughout the 52 week study period, participating women will complete the questionnaire and grip strength measurement a total of three times in order to assess their arthralgia while on AI therapy. Compliance with aromatase inhibitor (AI) therapy will also be assessed throughout the

Vitamin D for AIA

study to determine if AI compliance is improved in women who are receiving Vitamin D. Additionally, women will also have periodic assessments of serum 25-hydroxyvitamin D to assess whether vitamin D levels correlate with AIA, and to ensure that calcium and 25(OH) D levels are within healthy ranges.

SCHEMA

High Dose vs. Standard Dose Vitamin D for Aromatase Inhibitor-Induced Arthralgia

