6.5 Follow up at week 52, and End of Treatment Visit

The following assessments should be performed within five to ten business days of the completion of study therapy. End of treatment is defined as Week 52. These assessments should also be performed for patients who discontinue treatment prematurely (unless otherwise noted below).

- Measurement of body weight and BMI
- Laboratory assessments to include calcium level, 25-hydroxyvitamin D, and albumin.
- Patient is to complete the Health Assessment Questionnaire (HAQ-II)
- Grip strength measurement
- Record all concomitant medications added and/or changed.
- Assess compliance to aromatase inhibitor therapy
- Assess compliance to vitamin D and calcium treatment

Non-serious and serious adverse events should be recorded and graded appropriately as discussed in section 9.6.

At this point, patients will have completed study treatment and should proceed with the completion of their adjuvant therapy, as determined by the treating physician. Patients may take Vitamin D at any dosage they wish, at the discretion of the patient and the treating physician.

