12.1 Definitions

12.1.1 **Evaluable for toxicity:** All patients will be evaluable for toxicity from the time of their first treatment with Vitamin D.

12.1.2 **Evaluable for response:** All the patients who have been randomized will be considered evaluable for response, regardless of how much treatment they have received,

consistent with an intention to treat analysis. These patients will have their response classified according to the definitions stated below. Any patient who began the study medication, but does not complete the HAQ at 12 weeks, will be deemed to be a study failure (i.e. the development of AIA will be assumed), consistent with an intention to treat analysis.

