13.7 Futility Analysis

One interim analysis will be added to the study. It is expected to take place half-way through the study after 46 patients in each of the treatment group are enrolled and evaluable for the primary endpoint. The purpose of the interim analysis is to allow the study to stop early for lack of efficacy (futility). A non-binding O’Brien-Fleming spending function is used to calculate the futility boundary. Calculations were performed using nQuery Advisor + nTerim 3.0 (Statistical Solutions. Boston, MA).

The following table summarizes the futility boundary at each analysis when 50% and 100% patients are enrolled and evaluable at the interim analysis and the final analysis. The futility boundary in the term of p-value scale at the interim analysis is calculated as $p=0.47$ (or $Z=0.076$). If the one-tailed p-value exceeds 0.47, it will be recommended that the trial stop for futility.

Looks	Information	n per group	Futility Boundary (Z value)	Futility Boundary (one-tailed p value)
1	50%	46	0.076	0.47
2	100%	93	1.28	0.05

In order to preserve power and compensate for the interim futility analysis which tends to reduce power, the sample size of the study is increased from 88 per group to 93 per group, which is 196 total if considering a 5% drop out rate.

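### Enrolment is 186 in Sections 3 and 13.2 but 196 in Section 13.7, and at 5% dropout neither total gives the stated 80% power under the plan's own missing-questionnaire rule

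*Combined protocol and SAP*

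**What the plan says.** Three sections of the combined protocol and SAP give the sample size.

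- Section 3 says the size was "increased from 88 per group to 93 per group, which is 186 total if considering a 5% drop out rate", and then "A total of 186 patients at up to 5 centers will be randomized 1:1".
- Section 13.2 gives 93 per arm as the number needed for the chi-square test, and continues: "Assuming 5% dropout rate in the first 12 weeks, we will accrue 93 women to each arm, for a total of 186 women".
- Section 13.7 has Section 3's sentence again, with another total: "increased from 88 per group to 93 per group, which is 196 total if considering a 5% drop out rate".

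Sections 3 and 13.7 both give the loss of power from the interim futility look as the reason for going from 88 to 93. The Section 13.7 table treats 93 per group as enrolled and evaluable at the final analysis, and places the interim look "after 46 patients in each of the treatment group are enrolled and evaluable for the primary endpoint".

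Section 12.1.2 keeps every randomised woman in the analysis and adds: "Any patient who began the study medication, but does not complete the HAQ at 12 weeks, will be deemed to be a study failure". Such a woman is assumed to have developed AIA. No sample-size section mentions this rule.

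**The concern.** The total enrolment is a core design number, and the same sentence appears twice with different totals. A site, an IRB or the data review committee cannot tell from the text which total already includes the 5% dropout.

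There is also a question of what the 5% means. Dividing by 0.95 is right when dropouts leave the analysis and only reduce its size. Section 12.1.2 does something else: it keeps them and counts them as events. If dropout is equal in the two arms, this raises both event rates and narrows the 14-point difference the trial was sized to detect. The stated 80% power would then not hold at either total. With equal dropout the type I error is not affected; what is at stake is power, and an honest statement of it.

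**Working it through.** **Inputs.** From Section 13.2: AIA rates 33% (standard dose) and 19% (high dose), one-sided α = 0.10, power 80%, 5% dropout by week 12. From Section 13.7: a non-binding futility boundary of Z = 0.076 at 46 per group and a final critical value of Z = 1.28. From Section 12.1.2: a missing week-12 questionnaire after starting medication counts as AIA.

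**1. The plan's 88.** With p̄ = (0.33 + 0.19)/2 = 0.26,

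n = [1.2816·√(2·0.26·0.74) + 0.8416·√(0.33·0.67 + 0.19·0.81)]² / 0.14² = (0.795 + 0.515)² / 0.0196 = 87.6, so **88 per arm**. No dropout is included.

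**2. The plan's 93.** O'Brien-Fleming-type spending of β = 0.20 at half the information spends 2[1 − Φ(1.2816/√0.5)] = 0.0699. This gives the boundary Z = 0.076 and an inflation factor of 1.0695: 87.6 × 1.0695 = 93.7. The plan uses 93, and exact binomial power at 93 per arm with the boundary followed is 80.0%. So 93 is the evaluable number for 80% power with the futility look, as Sections 3 and 13.7 say.

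**3. The two totals.** 93/0.95 = 97.9, so 98 per arm and **196**. The other total is 2 × 93 = **186**, with no division by 0.95. If 5% of 93 leave the analysis, 93 × 0.95 = 88.35, so about 88 per arm remain.

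**4. The rule in Section 12.1.2.** With 5% missing in each arm:

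- standard dose: 0.95 × 0.33 + 0.05 = 0.3635
- high dose: 0.95 × 0.19 + 0.05 = 0.2305
- difference: 13.3 points instead of 14

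**5. Power.** Exact binomial, success if the final Z ≥ 1.2816, look at 46 per group. Because the boundary is non-binding, power is shown with the boundary followed and with it ignored.

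| Handling of dropouts | Enrolled | Analysed per arm | Followed | Ignored |
|---|---|---|---|---|
| Excluded, 5% per arm | 186 | 88 | 78.6% | 80.4% |
| Excluded, 5% per arm | 196 | 93 | 80.0% | 82.3% |
| Scored as AIA, 5% per arm | 186 | 93 | 73.8% | 76.2% |
| Scored as AIA, 5% per arm | 196 | 98 | 74.7% | 77.5% |
| Half of the 5% scored as AIA | 186 | 93 | 77.0% | 79.4% |
| Half of the 5% scored as AIA | 196 | 98 | 77.8% | 80.5% |
| Scored as AIA, 4% standard / 6% high dose | 186 | 93 | 66.2% | 68.7% |
| Scored as AIA, 6% standard / 4% high dose | 186 | 93 | 80.5% | 82.7% |

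Moving the look to 49 per group at 196 changes 74.7% to 75.3%.

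**6. Number that would restore 80%.** With 36.35% versus 23.05%, a design without a look needs 106 per arm (212). With the futility look it needs 113 per arm (226); exact power there is 80.3% with the look at 56 per arm. No further division by 0.95 applies, because the missing women stay in the denominator.

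**The case against.** The strongest reply is that the working target is readable: both sentences that say what will be done, in Sections 3 and 13.2, give 186, and 196 appears once, in the futility section. That makes 186 the likelier intention. It does not remove the conflict, since 196 is exactly what Section 13.7's reasoning yields.

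A second reply is that 88/0.95 = 92.6, so 93 per arm is also the fixed-design size inflated for 5% dropout, and Section 13.2 can be read that way. This probably explains how 186 arose. But the same five women per arm cannot serve both as the dropout allowance and as the futility allowance, and Sections 3 and 13.7 have already assigned them to futility.

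Third, inflating for dropout and scoring dropouts as AIA are alternatives. Under Section 12.1.2, 93 enrolled is about 93 analysed, so the missing division by 0.95 is not then a loss of numbers. This stands: on that rule the shortfall comes from the narrowed difference instead, and the two losses must not be added.

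Fourth, ten women move power by only about 1 to 2 points, and the larger drop depends on assumptions. That also stands, and it is why the power figures call for disclosure while the conflicting total calls for correction.

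Finally, Section 6.5 says of the end-of-treatment assessments, which include the questionnaire: "These assessments should also be performed for patients who discontinue treatment prematurely". Some early stoppers may therefore have data. But that visit is tied to the end of therapy, not to week 12, so a woman who stops at week 6 could complete it and still be scored as AIA.

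**Conclusion.** The concern holds. The enrolment totals contradict each other, and this rests on no assumption. On the plan's own account of the step from 88 to 93, 186 contains no dropout allowance and 196 does.

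The power conclusion is conditional. If dropout is 5% in each arm, all dropouts began medication and lack the week-12 questionnaire, and the 33% and 19% planning rates exclude dropouts, then power is 73.8% to 76.2% with 186 and 74.7% to 77.5% with 196. The shortfall from 80% with the boundary followed is about 6 points at 186 and 5 points at 196. The documents do not say whether the planning rates already count missing women as AIA. A one-point shift of dropout in each arm, in opposite directions, moves power at 186 to between 66% and 83%, so equal dropout is the assumption that matters most.

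**What to change.** Required: put one total in Sections 3, 13.2 and 13.7, and say in Section 13.2 that 93 per arm is the evaluable number, already raised from 88 for the interim look.

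- If 186 is kept, remove the claim that it covers 5% dropout and add wording such as: *With 5% dropout per arm scored as AIA under Section 12.1.2, power is about 74% if the futility boundary is followed and about 76% if it is not.* This costs only wording and a less favourable stated power.
- If 196 is meant, correct Sections 3 and 13.2 and state about 75% to 77%. This adds ten women, or 10/6 to 10/4 = 1.7 to 2.5 months at the planned 4 to 6 per month.

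Neither option restores 80% on these assumptions. If the sponsor wants 80% under Section 12.1.2, the figure is 226, which is 40 more than 186 and takes 40/6 to 40/4 = about 7 to 10 months more.

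Whichever total is chosen, list the assumptions beside the power statement (equal dropout by arm, dropouts started medication and have no week-12 questionnaire, planning rates exclude dropouts) and show the range under unequal dropout. Define dropout, and say whether a questionnaire completed at an early-termination visit under Section 6.5 counts as the week-12 assessment. Section 12.1.2 should also say how a woman who was randomised but never started medication is classified.
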